13.2 Sample Size/Accrual Rate

For the primary endpoint of overall response rate with the parameters as noted in section 13.1, a total sample size of 37 patients is needed in a two-stage design with 12 patients in the first stage and 25 patients in the second stage for Cohort A. For Cohort B, a total sample size of 25 patients is needed in a two-stage design with 8 patients in the first stage and 17 patients in the second stage. A minimum accrual rate is expected to be 3 subjects per month. With a minimal accrual rate of 3 subjects per month, we expect the study enrollment to last approximately 9 months.

PLANNED ENROLLMENT REPORT- COHORT A (Closed to Accrual)

| Racial Categories | Ethnic Categories | | | | Total |
|--------------------------------|------------------------|------|--------------------|------|-------|
| | Not Hispanic or Latino | | Hispanic or Latino | | |
| | Female | Male | Female | Male | |
| American Indian/ Alaska Native | 1 | NA | — | NA | 1 |
| Asian | 1 | NA | — | NA | 1 |

| Racial Categories | Ethnic Categories | | | | Total |
|---|-------------------------------|-------------|---------------------------|-------------|--------------|
| | Not Hispanic or Latino | | Hispanic or Latino | | |
| | Female | Male | Female | Male | |
| Native Hawaiian or Other Pacific Islander | 1 | NA | — | NA | 1 |
| Black or African American | 1 | NA | 1 | NA | 2 |
| White | 31 | NA | 1 | NA | 32 |
| More Than One Race | — | NA | — | NA | — |
| Total | 35 | — | 2 | — | 37 |

PHS 398 / PHS 2590 (Rev. 08/12 Approved Through 8/31/2015)

OMB No. 0925-0001/0002

PLANNED ENROLLMENT REPORT- COHORT B

| Racial Categories | Ethnic Categories | | | | Total |
|---|------------------------|------|--------------------|------|-----------|
| | Not Hispanic or Latino | | Hispanic or Latino | | |
| | Female | Male | Female | Male | |
| American Indian/ Alaska Native | 1 | NA | — | NA | 1 |
| Asian | 1 | NA | — | NA | 1 |
| Native Hawaiian or Other Pacific Islander | 1 | NA | — | NA | 1 |
| Black or African American | 1 | NA | 1 | NA | 2 |
| White | 19 | NA | 1 | NA | 20 |
| More Than One Race | — | NA | — | NA | — |
| Total | 23 | — | 2 | — | 25 |

PHS 398 / PHS 2590 (Rev. 08/12 Approved Through 8/31/2015)

OMB No. 0925-0001/0002

13.3 Stratification Factors

There are no planned stratification factors in this study.

13.4 Analysis of Secondary Endpoints

COHORT A – SECONDARY ENDPOINTS

We will also assess toxicity in patients with ULMS treated with nivolumab. Among the first phase of 12 patients, there is at least 58% probability of observing one or more rare (7% true probability) events, and 83% probability of observing toxicities that have a true occurrence of at least 15%. Among the total cohort of 37 patients, there is at least 85% probability of observing one or more rare (5% true probability) events, and 95% probability of observing toxicities that have a true occurrence of at least 8%. With 37 treated patients, the maximum width of a 90% two-sided exact binomial confidence interval for any estimated adverse event proportion will be no wider than $\pm 14\%$.

Rate of Progression-free survival at 12 weeks with a null hypothesis of 20% and an alternative hypothesis of 40% at 12 weeks will be investigated. Patients lost to follow-up or deaths within 12 weeks will be counted as failures. The overall power for overall progression-free rate at 12 weeks is 87%, using the exact binomial distribution. The

operating characteristics of this design are calculated using a one-sided exact test with 10% type I error.

COHORT B – SECONDARY ENDPOINTS

Toxicity: Among the first phase of 8 patients, there is at least 57% probability of observing one or more rare (10% true probability) events, and 73% probability of observing one or more toxicities that have a true occurrence rate as low as 15%. Among the total cohort of 25 patients, there is at least 84% probability of observing one or more rare (7% true probability) events, and 93% probability of observing toxicities that have a true occurrence of at least 10%. With 25 treated patients, the maximum width of a 90% two-sided exact binomial confidence interval for any estimated adverse event proportion will be no wider than $\pm 18\%$.

Rate of Progression-free survival at 6 months with a null hypothesis of 18% and an alternative hypothesis of 40% at 6 months will be investigated. Patients lost to follow-up or deaths within 6 months will be counted as failures. The overall power for overall progression-free rate at 6 months is 85%, using the exact binomial distribution. The operating characteristics of this design are calculated using a one-sided exact test with 10% type I error.

In addition, we will explore the relationship between integrated biomarkers PDL1/PD1/PD2 status (PDL1 status, PDL1 in infiltrating lymphocytes, PD2 status in archival tumor) and response to combination treatment of nivolumab and ipilimumab. We will use Fisher's Exact Test to assess the relationship between each biomarker and response to combination treatment of nivolumab and ipilimumab. Each is expected to have similar characteristics. For example, with this design, assuming tissue is available on 90% of the sample, the probability of concluding combination treatment of nivolumab and ipilimumab response is related to the exploratory biomarker is 80%; given the unknown true response is 55% and 4% in positive marker versus negative marker patients, respectively, assuming 33% of the population is over-expressed for PDL1. The power to detect the relationship of interest increases as the prevalence of the biomarker increases. The operating characteristics of this design are calculated using a two-sided exact test with 10% type I error.

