13 STATISTICAL CONSIDERATIONS

13.1 Study Design/Endpoints

COHORT A - Study Design and Endpoints

This is a phase II two-stage clinical trial with a primary endpoint of objective response per RECISTS 1.1 among patients with advanced ULMS treated with nivolumab.

For the primary endpoint of overall response with a null hypothesis of 5% and an alternative hypothesis of 20% we would need 37 patients in a two-stage design with 12 patients in the first stage and 25 patients in the second stage. At the first stage analysis we will assess overall response, we will need to observe at least 1 response out of 12 patients to continue through the second stage. At the second stage we will assess overall response rate again, and we will need to observe at least 4 responses out of 37 patients to accept the treatment. The overall power for overall response rate is 90%. The overall type I error, the chance of incorrectly rejecting the null hypothesis is 9%. The probability of stopping at the first stage under the null hypothesis is 54%. The operating characteristics of this design are calculated using the exact binomial distribution. Subjects who continue treatment beyond initial investigator-assessed, RECIST 1.1-defined the initial progression event but may be designated as delayed responses for purposes of determining ORR and counted as responses for two stage designs.

Paired immediate pre-treatment and post- treatment biopsies will be obtained whenever possible in consenting patients, and in a minimum of 10 patients. If less than 10 patients have provided paired tumor biopsies, the remaining slots will give priority to obtain biopsies in the last group of 10 patients prior to completion of accrual. For the primary endpoint of overall response rate with the parameters as noted in section 13.1, a total sample size of 37 patients is needed in a two-stage design with 12 patients in the first stage and 25 patients in the second stage. A minimum accrual rate is expected to be 3 subjects per month. With a minimal accrual rate of 3 subjects per month, we expect the study enrollment to last approximately 13 months.

For Cohort A, 12 participants were accrued to the first stage. Since an objective response was not seen in the first stage of Cohort A, enrollment to the second stage did not begin.

COHORT B – Study Design and Endpoints

This phase II two-stage clinical trial will include patients with advanced ULMS treated with

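### Section 13.4 still gives Cohort A's 12-week PFS power (87%) and toxicity precision (±14%) for 37 patients, but the cohort closed at 12, where they are 56% and ±25.5 points

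*Combined protocol and SAP*

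**What the plan says.** Section 1.2 keeps PFS and toxicity under nivolumab alone as secondary objectives. In Section 13.1 the Cohort A response design reads "we would need 37 patients in a two-stage design with 12 patients in the first stage and 25 patients in the second stage". The same section then gives the outcome: "For Cohort A, 12 participants were accrued to the first stage", and "Since an objective response was not seen in the first stage of Cohort A, enrollment to the second stage did not begin".

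The Cohort A part of Section 13.4 is still written as a plan for the future. It sets a 12-week progression-free rate of 20% against 40%, tested one-sided by the exact binomial at 10%, with losses to follow-up and deaths before 12 weeks counted as failures. It then states "The overall power for overall progression-free rate at 12 weeks is 87" per cent, without giving a sample size. For toxicity, the precision statement begins "With 37 treated patients, the maximum width of a 90% two-sided exact binomial confidence interval" and puts the bound at ±14%. For the first 12 patients it gives a 58% chance of seeing an event with a 7% true rate, and "83% probability of observing toxicities that have a true occurrence of at least 15" per cent.

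**The concern.** The protocol was amended after Cohort A closed: Section 2.5 reports no responses and introduces Cohort B, and Sections 5.1.1 and 13.1 record the closure. The Cohort A secondary analyses were not brought into line. A reader who goes to Section 13.4 for the properties of the nivolumab-alone PFS analysis finds 87% power, and nothing there says that the figure needs 25 patients who were never enrolled.

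What is at stake is interpretation. If the 12-week test is not significant and is read against 87% power, it looks like fair evidence that the rate is below 40%. If the test has far less power, it is weak evidence. Toxicity rates quoted with ±14% precision would likewise look better determined than they are.

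**Working it through.** **Inputs.** Planned n = 37 and actual n = 12 (Section 13.1). Null 20%, alternative 40%, one-sided exact test at 10%, 90% two-sided exact interval (Section 13.4, Cohort A). Losses and early deaths count as failures, so the denominator is all patients.

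**1. The PFS test.** The critical value r is the smallest count with P(X ≥ r; n, 0.20) ≤ 0.10. Power is P(X ≥ r; n, 0.40), where P(X ≥ r; n, p) = Σ C(n,k) p^k (1−p)^(n−k) for k from r to n.

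| n | r | alpha at r | alpha at r − 1 | power at 40% |
|---|---|---|---|---|
| 37 | 12 | 5.2% | 10.5% (too large) | 86.7% |
| 12 | 5 | 7.3% | 20.5% (too large) | 56.2% |

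The first row reproduces the stated 87%. Neighbouring sizes do not: 35, 36, 38, 39 and 40 patients give 88.8%, 91.0%, 89.1%, 91.2% and 92.9%. So the figure belongs to the full 37-patient cohort. At 12 patients a true rate of 40% would be missed with probability 1 − 0.562 = 44%.

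**2. Toxicity precision.** The 90% Clopper-Pearson limits for x events in n are the 5% quantile of Beta(x, n−x+1) and the 95% quantile of Beta(x+1, n−x). I took the largest half-width over x.

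- n = 37: widest at x = 19, limits 36.8% to 65.7%, full width 28.9 points, half-width 14.46.
- n = 12: widest at x = 6, limits 24.5% to 75.5%, full width 50.9 points, half-width 25.47.

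Reading ± as half the full width fits Cohort B, where n = 25 gives 17.7 against a stated bound of ±18. On the same reading the Cohort A bound at 37 should be ±14.5, since 14.46 exceeds 14.

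**3. Chance of seeing at least one event**, 1 − (1−p)^n.

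- n = 12, p = 7%: 58.1% (stated 58%).
- n = 12, p = 15%: 1 − 0.85^12 = 85.8% (stated 83%).
- n = 37, p = 5%: 85.0% (stated 85%).
- n = 37, p = 8%: 95.4% (stated 95%).

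The four Cohort B figures also reproduce (57.0%, 72.8%, 83.7% and 92.8%, against 57, 73, 84 and 93). The 83% is the only one that does not; it is the value for 11 patients (1 − 0.85^11 = 83.3%).

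**The case against.** The 87% is not a miscalculation. It is a correct design-stage figure for a cohort that reached its second stage, and the documents disclose the early stop several times (Sections 2.5, 5.1.1, 9.1.1.1 and 13.1). Keeping the original design beside the recorded outcome is also the document's habit: the 37-patient enrolment table stays in Section 13.2 under a closed-to-accrual label. No decision hangs on the PFS test, because the success rule is response alone and Cohort A has already failed it. The 5-of-12 cut-off is derived here and is not in the plan. If the words at least, attached to the 58%, are meant to govern the 83% too, then 85.8% does not contradict it.

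Most of this stands, and it limits the weight of the point. It does not remove it. Section 13.4 has no label like the one in Section 13.2, and it describes the test as still to come without giving its properties at 12 patients. Even on the generous reading, 83% is not what the formula gives, while every neighbouring figure is.

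A reader might also infer that the two cohorts' PFS nulls conflict, since Cohort B's plan begins "Rate of Progression-free survival at 6 months with a null hypothesis of 18" per cent, close to Cohort A's 20% at 12 weeks. The documents do not support that. The time points differ, and a rate of 20% at 12 weeks can precede 18% at 6 months. The documents do not say that the nulls share a historical population, and they give no hazard shape. Under constant hazard, 18% at 6 months would imply about 45% at 12 weeks, and a 71% chance of at least 5 of 12; a Weibull shape of 0.5 gives 31% for both. The calendars in Section 10 also scan every 12 weeks in Cohort A and every 8 in Cohort B.

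**Conclusion.** The point holds as a missed update with one small arithmetic slip. For the 12 patients enrolled, the planned test has 56% power, not 87%, and the toxicity bound is ±25.5 points, not ±14. The 83% should be 86%, and the original 37-patient bound is ±14.5. These results assume that all 12 patients are in the denominator, that the test keeps its stated nulls and 10% level, and that ± means half the interval width. No hazard model is needed.

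A reader might go further and conclude that the test should be removed. That is not warranted. Accrual ended in October 2015 and this version already provides for CTCAE 5.0 from April 2018, so the 12-week outcomes already exist. Deleting a prespecified test now would be a post-data change, and accurate labelling solves the problem without it.

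**What to change.** In the Cohort A part of Section 13.4:

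- Label the 37-patient power, precision and detection figures as the original design, which was not reached.
- State the properties at 12 patients: reject at 5 or more of 12, attained alpha 7.3%, power 56%.
- Report the proportion progression-free at 12 weeks primarily as an estimate with an exact 90% interval, so that a non-significant result is not read against 87% power. Add that this interval and the 10% one-sided test need not agree: at 5 of 12 the p-value of 7.3% exceeds 5%, so the interval still includes 20%.
- Give toxicity precision as up to ±25.5 points for 12 patients, and ±14.5 for the original 37.
- Correct 83% to 86%.

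This changes wording only and needs no new data or visits. The cost is that the stated power and precision become visibly less favourable.

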nivolumab and ipilimumab with a primary endpoint of objective response per RECISTS 1.1 among

For the primary endpoint of overall response with a null hypothesis of 5% and an alternative hypothesis of 30% we would need 25 patients in a two-stage design with 8 patients in the first stage and 17 patients in the second stage. At the first stage analysis we will assess overall response, we will need to observe at least 1 response out of 8 patients to continue through the second stage. At the second stage, we will assess overall response rate again, and we will need to observe at least 3 responses out of 25 patients to accept the treatment. The overall power for overall response rate is 94%. The overall type I error, the chance of incorrectly rejecting the null hypothesis is 9%. The probability of stopping at the first stage under the null hypothesis is 66%. The operating characteristics of this design are calculated using the exact binomial distribution.

Subjects who continue treatment beyond initial investigator-assessed, RECIST 1.1-defined progression will be considered to have investigator-assessed progressive disease at the time of the initial progression event but may be designated as delayed responses for purposes of determining ORR and counted as responses for two stage designs.

In order to assess the impact of immune checkpoint inhibition in this population, tissue will be acquired to analyze the integrated biomarkers and determine the potential drug effect in this disease. Biomarkers will be assessed from pre-treatment and post-treatment biopsies collected in a minimum of 10 patients on this study. During enrollment to Cohort A, one set of pre-treatment and post-treatment biopsies was collected; the additional 9 were not performed because the study did not progress to Stage II. In Cohort B, paired immediate pre-treatment and post-treatment biopsies will be collected in the first eight participants who enroll to the study (stage 1-Cohort B). For this cohort, participants are required to have disease that can be biopsied safely, as discussed in Section 3.1.11. Biopsies will be optional among participants enrolled in the second stage of cohort B.

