13.6.2 Evaluation of Response

All eligible patients included in the study must be assessed for response to treatment, even if there are major protocol treatment deviations or if they are ineligible. Each patient will be assigned one of the following categories: 1) complete response, 2) partial response, 3) stable disease, 4) progressive disease, 5) early death from malignant disease, 6) early death from toxicity, 7) early death because of other cause, or 9) unknown (not assessable, insufficient data). [Note: By arbitrary convention, category 9 usually designates the “unknown” status of any type of data in a clinical database.]

All of the patients who met the eligibility criteria (with the possible exception of those who received no study medication) should be included in the main analysis of the response rate. Patients in response categories 4-9 should be considered to have a treatment failure (disease progression). Thus, an incorrect treatment schedule or drug administration does not result in exclusion from the analysis of the response rate. Precise definitions for categories 4-9 will be protocol specific.

All conclusions should be based on all eligible patients. Subanalyses may then be performed on the basis of a subset of patients, excluding those for whom major protocol deviations have been identified (e.g., early death due to other reasons, early discontinuation of treatment, major protocol violations, etc.). However, these subanalyses may not serve as the basis for drawing conclusions concerning treatment efficacy, and the reasons for excluding patients from the analysis should be clearly reported. The 95% confidence intervals should also be provided.

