14.1.2 Closed to Accrual

The study status is (permanently) Closed to Accrual when no more patient enrollment slots are available, and at least one patient is still actively receiving the study treatment. Sites are no longer permitted to enroll additional patients.

Patient slots are no longer available when the following criteria are met:

- The pre-specified number of evaluable patients has been successfully enrolled, treated, and evaluated.
- The study treatment has failed to meet the pre-specified efficacy goal at the stage 1 interim analysis.
- CTEP and the investigators agree that unacceptable toxicities preclude further enrollment.

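### The 85% overall power for 6-month PFS in Cohort B assumes all 25 patients are enrolled; with the stage 1 response rule it is 80–81%

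*Combined protocol and SAP*

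**What the plan says.** Section 13.4, Cohort B, sets a null 6-month progression-free rate of 18% against 40%, with a one-sided exact test at 10%. Losses to follow-up and deaths within 6 months count as failures. On power it says: "The overall power for overall progression-free rate at 6 months is 85%, using the exact binomial distribution". It gives neither the number of patients nor the rejection cutoff behind that figure.

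Section 13.1, Cohort B, describes 8 patients in stage 1 and 17 in stage 2. The rule between them concerns response, not PFS: "we will need to observe at least 1 response out of 8 patients to continue through the second stage". For response (5% against 30%, accept at 3 or more of 25) it says "The overall power for overall response rate is 94" percent, and "The probability of stopping at the first stage under the null hypothesis is 66" percent. Section 14.1.2 lists among the grounds for permanent closure to accrual: "The study treatment has failed to meet the pre-specified efficacy goal at the stage 1 interim analysis".

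The toxicity paragraph of 13.4 keeps the two cohort sizes apart: "Among the first phase of 8 patients, there is at least 57% probability" for stage 1, and "With 25 treated patients, the maximum width of a 90% two-sided exact binomial confidence interval" for the full cohort. The PFS sentence makes no such distinction. I found no statement that the 85% is conditional on reaching 25 patients, and none on how 6-month PFS is handled if the cohort stops at 8.

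**The concern.** The plan uses the same term, overall power, for two Cohort B endpoints. For response it is the chance of success from the first patient onward, with the possibility of stopping at 8 included. A reader will take the PFS figure the same way. If it is really the power of a 25-patient test, it leaves out the trials in which that test is never run.

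The stop is part of the design, with a probability that the plan itself states under the response null. Cohort A ended at its own stage 1 rule. What is at stake is modest but real: 13.4 may promise a chance of a positive PFS finding that the design does not have.

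**Working it through.** **Inputs.** From 13.4: PFS 18% and 40%, one-sided exact test at 10%. From 13.1 and 13.2: 8 + 17 = 25 patients; continue if at least 1 of 8 responds; response rate 5% and 30%; accept at 3 or more of 25. Two inputs are not in the documents and are assumed: how response and 6-month PFS are associated, and that a cohort stopped at 8 makes no PFS claim.

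**Step 1: reproduce the stated 85%.** Let X be the number progression-free at 6 months among 25.

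| Reject at | P(X ≥ cutoff), PFS 18% | P(X ≥ cutoff), PFS 40% |
|---|---|---|
| 7 of 25 | 14.9% | 92.6% |
| 8 of 25 | 6.6% | 84.6% |
| 9 of 25 | 2.5% | 72.6% |

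The smallest cutoff that keeps alpha within 10% is 8, and its power rounds to 85%. The stated figure is the fixed 25-patient power.

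**Step 2: what overall means for response.** The two-stage power at 30% (at least 1 of 8, then at least 3 of 25) is 93.8%. A fixed test of 3 or more of 25 would have 99.1%. The stated 94% therefore includes the stage 1 rule.

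**Step 3: chance that the 25-patient PFS test is run.** At a response rate of 30%, P(no response in 8) = 0.70^8 = 0.0576, so stage 1 is passed with probability 1 − 0.0576 = 0.942.

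**Step 4: overall PFS power.**

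P(stage 1 passed and X ≥ 8) = P(X ≥ 8) − 0.70^8 × P(X ≥ 8 given no responder in the first 8).

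Without a responder, each of the first 8 is progression-free with probability (0.40 − a)/0.70, where a is the probability of being both a responder and progression-free. The other 17 keep 0.40.

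- Independent: a = 0.30 × 0.40 = 0.12, so that probability stays at 0.40. Then 0.8464 − 0.0576 × 0.8464 = 0.798.
- Every responder progression-free: a = 0.30, so it is 0.10/0.70 = 0.143, and P(X ≥ 8 given no responder) = 0.569. Then 0.8464 − 0.0576 × 0.569 = 0.814.

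The overall power is 80–81%. A simulation of 1,000,000 trials gave 79.8% and 81.3%. With a cutoff of 7 and the stage 1 rule, the values are 87.3% and 88.4%, so neither of these cutoffs gives 85% once stage 1 is counted.

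**Step 5: allow a test on the stopped cohort.** The plan has none. The exact 8-patient test within 10% would reject at 4 or more of 8 (alpha 4.0%; 3 or more gives 16.1%). Adding it raises the total to 82.1% (independent) or 81.5% (every responder progression-free), still below 85%.

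**Step 6: power when the test is run.** 0.798/0.942 = 84.6% and 0.814/0.942 = 86.3%, that is, about 85–86%.

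**Step 7: type I error.** Passing stage 1 and reaching 8 of 25 cannot be more likely than reaching 8 of 25 alone. With no claim from a stopped cohort, the unconditional false-positive rate at PFS 18% is therefore at most 6.6%, inside the nominal 10%.

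**The case against.** The best defence is that the arithmetic in 13.4 is right for the test it describes. The PFS test has no interim rule of its own, quoting power at the planned sample size is common for a secondary endpoint, and anyone who has read 13.1 knows that 25 patients depends on stage 1. The convention is also consistent: Cohort A's 87% for 12-week PFS is likewise the full-sample figure (at least 12 of 37: alpha 5.2%, power 86.7%). All of this is true, and it makes the point one of labelling. It does not make either number an overall power, given that 13.1 uses the same term for a figure that counts the stop.

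A second objection is that 80–81% treats a stage 1 stop as no PFS success, which the documents do not say. That stands as an assumption and has to be stated with the figure; step 5 shows that relaxing it does not restore 85%.

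Third, the range is not a strict bound. Section 13.1 lets a patient with earlier RECIST progression count as a delayed responder, so response and 6-month PFS could in principle be negatively associated. In the implausible extreme where no responder is progression-free, the overall power is 79.2%, slightly lower again.

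A reader might also infer that the 25-patient test is itself underpowered, or that selection through stage 1 inflates its false-positive rate. Steps 6 and 7 do not support either: the test has about its stated power when it is run, and the design's error rate stays within the nominal level.

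**Conclusion.** The point holds as a misstated power. The 85% is correct as the power with all 25 patients enrolled. As an overall power, at a response rate of 30% and PFS of 40%, the figure is 80–81%, a shortfall of about 3 to 5 points. It rests on response and PFS being independent or positively associated, and on no PFS claim from a cohort stopped at 8.

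The scope is narrow. This is a secondary endpoint, no acceptance rule depends on it, and the primary response design reproduces as stated. A reader might be tempted to quote the much lower overall power that would apply if the response rate were well under 30%. Such values lie outside the alternative for which the plan claims power, so they do not show that the plan's figure is further wrong.

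**What to change.** In 13.4, Cohort B:

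- Label 85% as the power with all 25 patients enrolled, rejecting at 8 or more of 25 (attained alpha 6.6%). This also fixes the cutoff in advance.
- State the overall power allowing for the stage 1 rule as 80–81% at a response rate of 30% and PFS of 40%, with its assumption: a cohort stopped at 8 makes no PFS claim.
- Say that such a cohort reports 6-month PFS descriptively with an exact interval.

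The interval level is the team's choice. Section 13.6.2 says "The 95% confidence intervals should also be provided", but about the response rate, and 13.4 uses 90% for adverse events.

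The cost is a few sentences and a slightly less favourable stated figure. Sample size, stage 1 rule, data collection and primary analysis do not change.

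### The 80% power for the Cohort B biomarker test assumes that all 25 patients are enrolled; with the stage 1 stop, the chance of detecting the relation is about 70%

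*Combined protocol and SAP*

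**What the plan says.** Section 13.4 plans Fisher's exact test of each marker against response to the combination, and says the markers should behave similarly. Its worked example is for PD-L1, "assuming tissue is available on 90% of the sample" and "given the unknown true response is 55% and 4% in positive marker versus negative marker patients, respectively, assuming 33% of the population is over-expressed". With a two-sided exact test at 10%, it reports that "the probability of concluding combination treatment of nivolumab and ipilimumab response is related to the exploratory biomarker is 80" per cent. It ties this to the present design, and does not mention stopping after stage 1.

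Section 13.1 sets the Cohort B design: "we would need 25 patients in a two-stage design with 8 patients in the first stage and 17 patients in the second stage", and "we will need to observe at least 1 response out of 8 patients to continue through the second stage". Section 14.1.2 lists among the grounds for permanent closure to accrual: "The study treatment has failed to meet the pre-specified efficacy goal at the stage 1 interim analysis". Section 13.1 also records that Cohort A had no response in 12 patients and never opened its second stage.

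Section 9.1.1.1 (assay performance) names the same test for the same markers against objective response, but sets two-sided significance at p<0.05.

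**The concern.** The outcome in the marker test is the same response that decides whether patients 9 to 25 are enrolled. Whenever the cohort stops at 0 of 8, every patient is a non-responder and the marker table carries no information. A power figure that describes the study as designed has to count those trials as non-detections.

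The scenario also carries its own stopping risk. A 55% versus 4% split at 33% prevalence is not the cohort's 30% alternative; it implies a lower overall response rate and so a higher chance of 0 of 8.

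At stake is how likely the study is to deliver a stated secondary objective. Section 9.1.1.1 says the PD-L1 result may serve as a stratification variable in later phase II trials, so someone planning on this study should know the real chance of obtaining it.

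**Working it through.** **Inputs.** From Section 13.1: 8 + 17 patients, continue if at least 1 of 8 responds. From Section 13.4: response 0.55 (marker-positive) and 0.04 (marker-negative), prevalence 0.33, tissue on 90%, two-sided Fisher exact test at 0.10. Tissue: 0.9 × 25 = 22.5, so 22 or 23 patients.

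**Step 1: reproduce the 80%.** Take the number of marker-positive patients as Binomial(n, 0.33), enumerate all response tables, and add the probabilities of those with p ≤ 0.10, with all 25 patients enrolled:

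- n = 22: 79.8%
- n = 23: 81.9%
- fixed split of 8 positive and 15 negative: 80.1%
- fixed split of 8 positive and 14 negative: 80.8%

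The stated 80% is recovered without any stage 1 stop. The primary design reproduces too (type I error 9.4%, power 93.8%, early stop 66.3% under the null), so the design is being read as intended.

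**Step 2: stopping risk in this scenario.**

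- Overall response = 0.33 × 0.55 + 0.67 × 0.04 = 0.1815 + 0.0268 = 0.2083
- P(0 of 8) = (1 − 0.2083)^8 = 0.7917^8 = 15.4%
- For comparison, at the 30% alternative: 0.70^8 = 5.8%

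**Step 3: power with the stop.** In a stopped cohort the table has no responders, p = 1, and rejection is impossible. So

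power with stop = power at full enrolment − P(0 of 8, and the full 25 would have rejected),

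power given stage 2 = power with stop / (1 − 0.154).

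The results by exact enumeration are below. "Stage 1/stage 2" is written here as the number with tissue in each stage.

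| With tissue (stage 1 / stage 2) | All 25 enrolled | With the stop | Given stage 2 opens |
|---|---|---|---|
| 22 (8/14) | 79.8% | 70.1% | 82.9% |
| 22 (7/15) | 79.8% | 69.7% | 82.4% |
| 23 (8/15) | 81.9% | 71.8% | 84.9% |
| 23 (7/16) | 81.9% | 71.4% | 84.4% |

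A 200,000-run simulation agreed. The simple product 0.80 × 0.846 = 67.7% is a little too low, because the stopped cohorts would have had lower power anyway (about 63% to 68%).

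**Step 4: sensitivity.** Fixing the marker-positive count at 8 gives 71.5% to 72.3% with the stop for 8 versus 15, and 73.8% for 8 versus 14. Fixing it at 7 gives about 75% to 76% with the stop, but 87% to 88% without, so that is not how the 80% arose. The only variant near 80% with the stop is 8 versus 17 with tissue on all 25 (79.1%), which contradicts the 90% tissue assumption.

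**Step 5: the 5% level of Section 9.1.1.1.** The same calculation at p ≤ 0.05 gives 69.6% (22) and 72.8% (23) at full enrolment, 61.4% to 64.6% with the stop, and about 73% to 76% given that stage 2 opens (0.614/0.846 = 72.6%; 0.646/0.846 = 76.4%).

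**The case against.** The best defence is that the 80% is correctly calculated from its inputs and is meant to apply to a fully enrolled cohort. Section 13.4 also quotes toxicity probabilities for the total cohort of 25 without discounting for early stopping, and its reference to the design may mean no more than the test set-up. The analysis is exploratory, the rates are described as unknown and offered as an example, and the sample size comes only from the primary response rule.

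Much of this stands: the arithmetic is sound and nothing else in the plan rests on the figure. But the condition is not written. The toxicity text separates the first 8 patients from the full 25; the biomarker text does not. Nor is 80% the conditional figure: once stage 2 is known to have opened, power is 82% to 85%. The 80% describes a trial without an interim stop.

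A reader might infer that a null marker result would be less informative than the plan suggests. The documents do not support that. A null result that anyone would interpret can arise only after stage 2 opens, where power is slightly above 80%. A cohort stopped at 0 of 8 gives no marker comparison and cannot be mistaken for a negative one.

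A reader might also lower the figure further by applying Cohort A's archival tissue yield (10 of 12, Section 9.1.1.1). That is a poor guide: Sections 3.1.11 and 13.1 require accessible tumour and paired biopsies in the first eight Cohort B patients, which Cohort A did not.

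**Conclusion.** The point holds as a statement about planning probability. Under the two-stage design and the plan's own scenario, the chance of detecting the marker-response relation is about 70% (69.7% to 71.8%) rather than 80%. The roughly 30% chance of non-detection is made up of about 15% in which the cohort stops and no test is possible, and about 15% in which stage 2 opens but the test misses. Given that stage 2 opens, power is about 82% to 85%.

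This rests on the plan's 55%, 4% and 33%, tissue on 22 or 23 of 25, a random marker count, a two-sided 10% test, and the stage 1 rule applied as written. At the 5% level of Section 9.1.1.1, the figures are about 61% to 65% overall and 73% to 76% given stage 2. The primary response decision, its error rates and the sample size are not affected.

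**What to change.** In Section 13.4, replace the single 80% with three figures at the two-sided 10% level: about 70% overall under the two-stage design; about 83% if stage 2 opens; and about a 15% chance that the cohort stops at 0 of 8 and the test cannot be done. Add that the scenario implies a 20.8% overall response rate.

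Before doing so, choose one significance level for this test, since Section 13.4 uses 10% and Section 9.1.1.1 uses 5%, and report the figures that match.

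The cost is a sentence or two of text and a less favourable secondary power figure. The sample size, tissue collection, test and procedures stay as they are.
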